(UF) are key tracts in LLD as they are components of cognitive, affective and default mode networks and contain monoamine neurotransmitter projections. Supporting our model, past work implicates CB and UF deficits in LLD (4-7) and our recently published data associates tract damage in the CB with poor antidepressant response (8).

This study has broad *significance* for elucidating how vascular factors influence the occurrence and course of LLD. It provides a scientific opportunity to use a neuroimaging finding of known pathology (WMLs) to examine how circuit deficits adversely affect antidepressant response. Importantly, clinical translation of this work may guide individualized treatment. Knowledge of circuit-response relationships may inform antidepressant selection or the identification of individuals likely to be treatment-refractory. We propose that we may translate this work into clinical use by linking impairment in circuits and tracts with performance on specific cognitive measures. Such measures can then be used as markers of focal tract damage.

2.0 RATIONALE and SPECIFIC AIMS:

In a cohort of 130 depressed elders we will test our **central hypotheses: a) focal CB and UF WMLs disrupt connectivity and function of connected regions and contribute to cognitive deficits and affective symptoms; and b) antidepressants acting on neurotransmitter systems projecting through these tracts will be less effective**. We will examine how novel measures of tract-specific WML volumes are associated with neural connectivity (using resting state fMRI), reactivity to cognitive & affective stimuli (using a fMRI task), & clinical presentation. After MRI, participants will be stratified by WML volume and randomized to blinded escitalopram (5HT) or placebo. Participants who do not remit in this initial phase will then receive open-label bupropion (DA/NE). These drugs affect different neurotransmitter systems with distinct projection pathways. This design will allow us to examine both drug and placebo responses while also testing whether discrete neural circuit deficits differentially affect drug response.

Specific Aim 1: To characterize the effect of cingulum bundle (CB) and uncinata fasciculus (UF) WMLs on

Protocol Version: 2.0

Protocol Date: 04/10/2020

tract connectivity, function of connected regions, and the cognitive and affective presentation of LLD (Fig 1&2).

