Hypothesis 1: Greater CB WML volume is associated with a) reduced resting-state connectivity of frontal, temporal, and cingulate regions and b) deficits in attention, memory and processing speed.

Hypothesis 2: Greater UF WML volume is associated with a) reduced resting state functional connectivity between frontocingulate and medial temporal regions, and b) greater depression severity and negativity bias.

Exploratory Hypothesis: Greater CB WML volume is associated with failure of anterior and posterior DMN nodes to deactivate during attentional components of the fMRI task. Greater UF WML volume is associated with greater medial temporal reactivity during affective components of the fMRI task.

Specific Aim 2: To determine whether deficits in tract structural / functional connectivity predict nonremission to antidepressant treatments and if these relationships vary based on antidepressant mechanism of action.

Hypothesis 3: Nonremission to escitalopram will be predicted by: a) greater WML volume in the CB and UF, and b) reduced resting functional connectivity between structures connected by the CB and UF. Greater WML severity and reduced functional connectivity in these tracts will not significantly predict response to placebo.

Hypothesis 4: Nonremission to bupropion will be predicted by a) greater WML volume in the UF but not CB, and b) reduced resting functional connectivity deficits between structures connected by the UF but not CB.

Exploratory Aims: **Expl. Aim 1)** To determine if specific cognitive measures may serve as markers of focal tract WML damage. **Expl. Aim 2)** To use whole-brain multimodal imaging approaches to examine how connectivity differences in other brain regions may also predict nonremission to antidepressants.

For exploratory analyses, we will also recruit 30 elders with no psychiatric history. Data from this population will help us understand whether our neural and cognitive findings in depression represent differences from what is seen in healthy aging, or whether our observations in depressed elders are within the range of normal aging. This will be important for data interpretation and planning for future projects.

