- 11) ECT in last 6 months
- 12) A failed therapeutic trial of escitalopram in the current depressive episode (defined as at least 6 weeks of treatment at a daily dose of 10mg or higher)
- 13) Known allergy or hypersensitivity to escitalopram or bupropion
- 14) Current or planned psychotherapy

We will additionally enroll up to 60 older adults with no history of psychiatric or neurological illness in order to have 40 subjects with MRI data. Data gathered from this cohort will assist us as we interpret data from the depressed cohort. Entry criteria will be similar to those of the depressed cohort, but adjusted to reflect we want to enroll individuals without any history of depression or other psychiatric illness.

Nondepressed Cohort:**Inclusion Criteria:**

- 1) Age 60 years or older.
- 2) Mini-Mental State Exam \geq 24.
- 3) Ability to read and write English.
- 4) MADRS score \leq 8

Exclusion Criteria:**Diagnostic Issues:**

- 1) Current or past diagnoses of any Axis I psychiatric disorders
- 2) Any use of illicit substances (such as marijuana or cocaine) or abuse of prescription medications (such as benzodiazepines or opiates) within the last three months.
- 3) Presence of acute suicidality
- 4) Current or past psychosis

Medical Issues:

- 5) Known primary neurological disorder, including dementia, brain tumors, epilepsy, Parkinson's disease, or demyelinating diseases
- 6) Chronic untreated medical disorders (including but not limited to hypertension, hyperlipidemia, fibromyalgia, hypothyroidism, or any medical disorder) where treatment is warranted
- 7) Any physical or intellectual disability affecting completion of assessments
- 8) MRI contraindications

Antidepressant Treatment Issues:

- 9) Any history of antidepressant treatment, including antidepressant medications, psychotherapy, or brain stimulation such as ECT. Brief couples / marital counseling, where the focus of treatment was not a psychiatric illness is allowable.

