8.1.d. Other Phenotypic Assessments: We will move beyond traditional diagnostic criteria for a broader examination of specific depressive symptoms. The following assessments will be administered at either the screening or baseline visit, then again after completing each 8-week study drug phase: Insomnia Severity Index (ISI), Ruminative Response Scale (RRS), Penn State Worry Questionnaire (PSWQ), Fatigue Severity Scale (FSS), and the Snaith-Hamilton Pleasure Scale (SHAPS), the PROMIS Applied Cognition Abilities Short

Form, the Type D Scale (DS-14) of negative affect, the Generalized Anxiety Disorder 7 item scale (GAD7) and the Attentional Control Scale. Also, the Perceived Stress Scale (PSS) and the Perceived Social Support/Conflict survey will be administered at the baseline visit.

8.2. Cognitive Assessments: Subjects are excluded for MMSE scores < 24 or a diagnosis of dementia.

Our cognitive domain assessment approach (**Table 1**) is published (21,113). We group the cognitive tasks into rationally motivated domains with reasonable internal consistency by Cronbach's alpha. We will create Z-scores for each task measure across participants and to create the domain score, sum the Z-scores of the tasks in that domain. Variables in which good performance is represented by lower values rather than higher values will be reverse scored so higher Z-scores represent better performance for all variables. This battery covers the range of cognitive deficits associated with poor antidepressant response in LLD (21,57,114).

Using Z-scores increases power but decreases sensitivity. Our primary cognitive outcomes will be the domain scores, but to improve sensitivity we will also examine performance on individual measures, particularly for Exploratory Aim 1.

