15.0 STATISTICAL CONSIDERATIONS

For **Aim 1**, inter-correlation matrices and scatter plots will be used to assess and visualize the patterns of association among the tract WML values and respective fMRI connectivity values. Multivariate analysis will be conducted using canonical correlation. Canonical correlation can accommodate more than one variable on both the independent and dependent sides of the general linear modeling equation and those variables may be either metric or nonmetric. In canonical analysis, the solution depends both on correlations among the variables in each set and on correlations among variables between sets. In a simultaneous process, underlying canonical variates (or factor loadings) comprising the WML values on the independent side will be constructed in such a way to maximize the correlations with canonical variates of the fMRI values on the dependent side. The same assumptions as those underlying multiple linear regression apply. Evaluations of normality, linearity, and homoscedasticity will be conducted, as will tests of multicollinearity and singularity of the underlying correlation matrices. Simple bivariate correlations and scatterplots will assist with describing and visually the patterns of association, canonical correlation will control for the inter-correlations among the WML and fMRI values will maximizing the correlation between the two sets. Covariates of *age, sex, and vascular risk* will be included with the WML measures. Effects of *MADRS and total brain WML volume* will also be examined. We will use a similar approach to examine how WML values are associated with clinical presentation. For Hypothesis 1, attention, memory, and processing speed scores will be on the dependent side. For Hyp. 2, BRISC and baseline MADRS scores will be on the dependent side.

For the fMRI emotional dot-probe task, we will examine how WMLs are associated with ROI activation(Exploratory Hyp). Specifically, we will examine how CB measures are associated with activity in DMN and CCN regions during the task's attentional component and how UF measures are associated with amygdala activity during the affective component. In this analysis WML measures will be on the "independent" side of the canonical correlation while fMRI activation values will be "dependent" side.

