We will use a similar approach for Exploratory Aim 1, where we examine how cognitive test performance may serve as a marker of WML tract damage. Including the previous covariates plus education, cognitive test results will be on the independent side with tract WML values on the dependent side.

Data from nondepressed elders will be integrated into the above analyses. We will test for group differences in the neuroimaging and cognitive measures described above. We will also include a group variable (depressed or not depressed) in analyses.

Aim 2 examines how tract measures predict remission. Following our previous approach (21), our definition of remission is MADRS ≤ 7 . Secondly, we will examine drug response (50% improvement on MADRS). Remission / response status for subjects with missing data will be estimated via multiple imputation

method assuming that dropouts are missing at random.

We will use two regression models to test for mediation while adjusting for baseline MADRS, age, sex, and vascular risk. To assess indirect effects of tract WML and FC measures as mediator variables, we will regress a potential mediator on a tract-based measure (an explanatory variable of interest). We will fit another model in which antidepressant remission or nonremission serves as outcome variable, and the potential mediator and tract-derived measure serve as covariates. The second model can be either logistic or linear regression model depending on the nature of outcome. The product of two beta coefficients corresponding to the tract-based measure in the first model and to the mediation variable in the second model will be assessed by constructing bootstrapped 95% confidence intervals (CI); statistically significant difference from zero implies that the relationship between the outcome and explanatory variable is mediated by the variable in question (127,128).

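### Exploratory Aim 1 sets no marker criterion and no optimism check, and its only multivariate analysis yields sizeable correlations even from uninformative cognitive tests

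*Combined protocol and SAP*

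**What the plan says.** Section 2.0 states the purpose of Exploratory Aim 1: "To determine if specific cognitive measures may serve as markers of focal tract WML damage". Section 1.0 gives the intended use in the clinic: "Such measures can then be used as markers of focal tract damage".

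Section 15.0 carries the Aim 1 method over to this aim. In that method the canonical variates "will be constructed in such a way to maximize the correlations with canonical variates" on the other side. For Exploratory Aim 1, "cognitive test results will be on the independent side with tract WML values on the dependent side", together with the Aim 1 covariates (age, sex, vascular risk) and education.

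Section 8.2 makes the domain scores the primary cognitive outcomes, but adds: "to improve sensitivity we will also examine performance on individual measures, particularly for Exploratory Aim 1". Table 1 lists the tests by domain.

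On sample size, Section 2.0 has "In a cohort of 130 depressed elders". Section 15.0 adds: "Data from nondepressed elders will be integrated into the above analyses". Section 4.0 recruits that group "in order to have 40 subjects with MRI data", whereas Section 2.0 speaks of 30.

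For this aim the documents mention no hold-out sample, cross-validation, permutation reference, shrinkage, named canonical test, multiplicity rule or threshold for calling a test a marker. Bootstrapping appears only for the Aim 2 mediation products.

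**The concern.** A marker is useful if it predicts tract damage in people who were not used to build it. Canonical correlation answers a different question: how closely the best-weighted mix of one set of variables can be made to match the best-weighted mix of the other, in the same people. With many tests and a modest sample, much of that match is fitted noise.

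There is a second difficulty. The covariates share a side with the tests. A high canonical correlation, or a significant overall test, may therefore reflect age or vascular risk and say nothing about cognition. With no stated criterion, a reader of the results has only the size of the correlation and the loadings to go by, and either could make an uninformative battery look promising for later work.

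**Working it through.** **1. The plan's own figures.** Section 15.1 gives power for Aim 1 only.
- For r = 0.30 and N = 130: atanh(0.30) × √127 = 0.3095 × 11.27 = 3.488, and Φ(3.488 − 1.960) = 0.937. The stated figure of more than 90% reproduces.
- For R2 = 0.06 with covariate R2 = 0.10: f² = 0.06/(1 − 0.06 − 0.10) = 0.0714. The noncentral F with one tested predictor and 3 to 5 covariates gives 83.7% to 84.3% (noncentrality on error degrees of freedom) or 85.6% (noncentrality on N). The stated 83% reproduces within about three points.

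Both figures concern a single association or a single predictor. Neither covers a battery fitted jointly.

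**2. Inputs for Exploratory Aim 1.**
- Tests (Table 1): 4 + 5 + 3 + 3 + 3 = 18, in five domains.
- Covariates on the same side: 4, so up to 18 + 4 = 22 variables.
- N: 130 depressed, or 130 + 30 = 160 to 130 + 40 = 170 if groups are pooled.
- Tract measures, q: not stated. Assumed range 1 to 6. Cingulum bundle and uncinate fasciculus alone give 2; anterior cingulum, posterior cingulum and uncinate on each side give 6. The preliminary-data table splits the cingulum by part and side.

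**3. In-sample association when nothing is associated.** For one tract, R2 follows Beta(p/2, (N − 1 − p)/2), with mean p/(N − 1). With 18 tests and N = 130 that is 18/129 = 0.14; with 22 variables it is 22/129 = 0.17. For q above 1 the first canonical correlation was simulated with independent normal variables, at least 2,000 datasets per setting. Under this null the result does not depend on how strongly the tests correlate with one another. Mean values:

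| Variables on the cognitive side | N | q = 1 | q = 2 | q = 6 |
|---|---|---|---|---|
| 18 tests | 130 | 0.37 | 0.42 | 0.52 |
| 18 tests | 160 | 0.33 | 0.38 | 0.47 |
| 18 tests | 170 | 0.32 | 0.37 | 0.45 |
| 18 tests + 4 covariates | 130 | 0.41 | 0.46 | 0.55 |
| 5 domain scores | 130 | 0.19 | 0.24 | 0.34 |
| 5 domain scores | 170 | 0.16 | 0.21 | 0.30 |

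With 18 tests, q = 2 and N = 130, the 5th to 95th percentiles are 0.34 to 0.50, and 99% of null datasets reach 0.30, the association size used in Section 15.1.

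**4. Out of sample.** Applying the fitted weights to a fresh sample of the same size gives a mean correlation of 0.00 in every setting.

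**5. Would an overall test help?** Bartlett's chi-square for Wilks' lambda rejects at the 0.05 level in about 4% to 6% of datasets when neither tests nor covariates are associated with WML. Now let the 18 tests remain uninformative and let age alone explain part of each tract's WML (assumed R2 of 0.10 to 0.20, not a figure from the documents). With 22 variables, two tract measures and N = 130, the same test rejects in 68% to 99% of datasets if the two tract volumes are independent given age. In a sensitivity run with a correlation of 0.5 between them given age, it rejects in 46% to 90%. All of these rejections occur with no cognitive information present.

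**The case against.** A reader might infer that the plan judges markers by the in-sample canonical fit. The documents do not say so. They say which variables go on which side and give no decision rule. The gap is a missing criterion, not a stated wrong one.

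A reader might also infer that all 18 tests certainly enter one model with 130 people. That is not fixed either. Domain scores are the primary cognitive outcomes, individual tests are additional, and the nondepressed group is to be included. The lower rows of the table allow for this: the null association shrinks but does not vanish.

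A third inference, that an uninformative battery would be carried forward, goes too far. Section 15.1 works at an alpha of 0.05, and an ordinary overall test would hold that level if nothing were associated. This objection stands for the full null. It does not rescue the analysis as described, because the covariates share the tests' side and the test cannot tell age from cognition. Nor does a global test say which measure is the marker.

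The Aim 1 approach also includes simple correlations and scatterplots, which escape the joint maximisation. They are not adjusted for age, however, and there would be 18 × 2 = 36 to 18 × 6 = 108 of them. At 0.05 that means 1.8 to 5.4 expected false positives, with no multiplicity rule.

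Finally, the aim is labelled exploratory and directs no treatment. That limits the weight of the point.

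**Conclusion.** The point holds in a limited form. As described, neither the size of the canonical correlation nor an overall test of it can show that cognition marks tract damage, and the plan supplies nothing else that would. With uninformative tests entered individually, an in-sample first canonical correlation of about 0.37 to 0.52 is to be expected across N = 130 to 170 and two to six tract measures. With domain scores it is about 0.21 to 0.34. The corresponding value in new people is about zero.

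These figures assume normal variables and joint entry of the tests, and the number of tract measures is assumed. The rejection rates in step 5 also depend on the assumed strength of the age effect and on how the tract volumes correlate. The conclusion does not change anywhere in the ranges examined. Because the aim is exploratory, the change is desirable but not critical.

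**What to change.** Keep the canonical analysis and its loadings as description, and base the marker conclusion on prediction:

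- State in advance the tract measures and whether tests or domain scores are used.
- For each tract's WML, fit a base model of age, sex, vascular risk and education, plus depression group if the groups are pooled.
- Add the cognitive measures by ridge or lasso, tuned within folds, and report the gain in R2 over the base model from repeated 10-fold cross-validation. Use this set-level gain only to say whether the battery carries information.
- Name a specific test only on its own cross-validated gain over the base model, with a permutation reference and multiplicity control across tests. A set-level gain must not qualify individual tests, since one informative test could carry the other 17.
- Give the set-level gain a permutation reference too. In a ridge simulation with 18 null tests, the gain exceeded zero in 6% to 7% of datasets, so being above zero is not by itself tighter error control than a global test. The advantage is that the gain isolates cognition from the covariates and measures accuracy in people not used for fitting.

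The cost is a little more analysis code and a smaller reported association. No new data, visits or participants are needed.

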**Title: Connectivity Affecting the Antidepressant Response (CAARE)
Study Protocol**

Clinicaltrials.gov Identifier: NCT02332291

NIH Grant: R01 MH102246

NIH Grant Title: Neural Connectivity Affecting the Antidepressant Response: Testing a Lesion Model

Document Date: 4/10/2020

Connectivity Affecting the Antidepressant Response (The CAARE study)

NIH Grant: R01 MH102246

NIH Grant Title: Neural Connectivity Affecting the Antidepressant Response: Testing a Lesion Model

Clinicaltrials.gov Identifier: NCT02332291

PI: [name], MHSc
Department of Psychiatry
Vanderbilt University Medical Center
[name]
[name]

1.0 BACKGROUND:

Individuals with late-life depression (LLD) experience high levels of disability, mortality, and poor responses to antidepressants. Age-related white matter disease is characteristic of LLD and contributes to these poor outcomes (1). Although the underlying mechanisms are not well established, white matter disease may contribute to LLD by adversely affecting cognitive, affective, and default mode networks. This project's primary goals are to characterize whether focal vascular damage to specific white matter tracts: a) affects neural circuit connectivity & function, b) influences clinical presentation, and c) predicts poor response to antidepressants.

The MRI hallmark of 'vascular depression' is significant ischemic white matter lesion (WML) severity (2), a finding associated with poor antidepressant outcomes. Despite observations of diffuse white matter disease in LLD, we propose in our "disconnection hypothesis" (3) that focal damage to fiber tracts negatively affects the function of connected regions, resultantly contributing to cognitive deficits and clinical symptoms such as depression severity and negativity bias. Focal WMLs may also reduce the likelihood of an antidepressant response *when the specific antidepressant used acts on neurotransmitter systems projecting through the damaged fiber tract*. This implies that the effect of tract damage on clinical response may *differ between drugs with different mechanism of action*. We propose that the **cingulum bundle (CB)** and **uncinate fasciculus**

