3.0 ANIMAL STUDIES & PREVIOUS HUMAN STUDIES

3.1. Late life depression and vascular disease: Late-life depression (**LLD**) is characterized by poor treatment responses along with increased morbidity, mortality and disability (9,10). A significant body of research supports the role of vascular disease in the pathogenesis of LLD. This informed the “*vascular depression*” hypothesis, which posits that vascular disease, characterized by greater diffuse hyperintense white matter lesion (**WML**) severity on MRI, may predispose to or perpetuate LLD (1-3). Although not all studies agree (11-15), greater WML severity is generally associated with poorer antidepressant response (16-21). In our disconnection hypothesis (3), we propose that the functional and clinical significance of WMLs depends on which neural circuits are disrupted.

3.2. Circuits in LLD: The uncinate fasciculus (**UF**) and cingulum bundle (**CB**) are critical fiber tracts within functional networks implicated in Major Depressive Disorder (MDD; **Table 1**; Sect A.3). The **UF** is involved in memory and emotional processing (22). It runs within the temporal stem and connects the amygdala and hippocampus with the medial and lateral orbitofrontal cortex (23-28). The **CB** is a pathway superior to the corpus callosum involved in attention, memory, and emotional regulation (29). It contains fibers originating from the cingulate gyrus, thalamus, and frontoparietal areas, projecting to other cingulate regions, the prefrontal cortex, presubiculum, precuneus, amygdala, and hippocampus (26,27,29-31).

Work from our group and others shows that LLD is associated with greater WML severity in discrete tracts including the cingulum bundle (CB) and uncinate fasciculus (UF) (4-7). Similarly, work using diffusion tensor imaging also associates depression with deficits in the UF (7,32-34) and CB (32,34). Similarly, our recently published data demonstrates that greater WML severity in the CB is associated with poor antidepressant response (8). These data support that damage to the CB and UF contributes to the occurrence and presentation of LLD.

3.2.a Functional Networks in LLD: Effect of WMLs:

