9.0. RANDOMIZATION & STUDY DRUG ADMINISTRATION

9.1. Randomization: After initial assessments, participants are randomized to double-blinded Phase 1 drug assignment (escitalopram or placebo). As our primary interest for Phase 1 is related to escitalopram response, we will allocate participants in a 2:1 drug-to-placebo ratio. Randomization will be conducted by the Vanderbilt Investigational Drug Service. Nondepressed individuals will not be randomized to study drug.

Randomization will be stratified by MRI measures of total cerebral WML volume. Our measurement of total WML volume is automated and available within 24 hours of the scan and subjects will be stratified as "high" or "low" total cerebral WML volume. Based on pilot data, we will use a cutoff of 3.86mL; this is the median 3T WML volume from a cohort of 145 depressed elders analyzed using our WML segmentation method. When we reach 50% enrollment, we will re-assess this cutoff based on study data and adjust if necessary.

If there are delays in scan processing, stratification will be determined using the Coffey-modified Fazekas visual rating scale (2), dichotomizing participants as "high" (2 or 3, confluence of foci) or "low" (0 or 1, absent or punctate foci).

MRI measures will only be used for stratification. They will not guide or determine treatment decisions.

9.2. Phase 1: Blinded Escitalopram or Placebo: We selected escitalopram due to its tolerability, ease of dosing, and lack of effects on dopamine and norepinephrine (115). The Vanderbilt IDS will prepare over-encapsulated escitalopram and matching placebo and maintain the blinded assignment in case of emergencies. Participants will receive one tablet (10mg or placebo) for at least 2 weeks. If tolerated, it can be increased to a target dose of two tablets (20mg) daily at the two-week study contact, but dosing changes will not be made at week 6 or later. For problems with tolerability, the dose can be reduced to the previous level, but not below one tablet daily.

9.3. Transition: After 8 weeks subjects will be assessed for remission (MADRS \leq 7). Those achieving remission will end their study participation. Those who are not remitted will have their Phase 1 drug tapered over a week to decrease the chance of discontinuation syndrome then progress to Phase 2.

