This approach will slightly differ for each study phase. For Phase 1, models will include drug arm (placebo or escitalopram). To examine for differences in how tract impairment affects remission in each arm, we will test for interactions between drug assignment and tract integrity (WML & FC). We will explore significant interactions in individual models. For subjects entering Phase 2, we will test for differences in tract integrity (WML & FC) between those originally assigned to escitalopram and placebo. If differences are observed, in models we will control for original Phase 1 cohort assignment. In exploratory models, we will use similar approaches to test for the additional effect of cognitive domain function (Table 5) on remission. We will also use this approach for Exploratory Aim 2 when we examine the effect of connectivity deficits in other tracts.

Importantly, the relationship between connectivity and antidepressant response may not be linear. It is possible that a ‘threshold’ must be crossed in order for tract connectivity deficits to influence response (3). To properly take into account nonlinear effect of a continuous predictor variable (e.g., WML, FC) on response variable (e.g., remission or nonremission) in the models, we will employ restricted cubic splines of the predictor. Statistical significance of the nonlinear terms via F-test implies that the relationship between the two measures of interest can be nonlinear.

15.1. Sample Size and Statistical Power:

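### The Aim 2 models for tract WML (H3a, H4a) leave out global lesion burden, so the plan gives no estimate of how much of a CB or UF association is specific to the tract

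*Combined protocol and SAP*

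**What the plan says.** The thesis in section 1.0 is focal: "focal damage to fiber tracts negatively affects the function of connected regions", even though diffuse disease is seen in late-life depression. Section 3.1 also reports a link between outcome and overall lesion severity: "Although not all studies agree (11-15), greater WML severity is generally associated with poorer antidepressant response (16-21".

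Overall burden then appears twice in the methods. Section 9.1: "Randomization will be stratified by MRI measures of total cerebral WML volume". Section 15.0, for Aim 1: "Effects of *MADRS and total brain WML volume* will also be examined".

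The Aim 2 text in section 15.0 does not mention it. The covariates are given by "We will use two regression models to test for mediation while adjusting for baseline MADRS, age, sex, and vascular risk". Drug arm is added in Phase 1. Original assignment is added in Phase 2 if tract measures differ between the original arms. For Phase 1, "we will test for interactions between drug assignment and tract integrity (WML & FC", followed by "We will explore significant interactions in individual models". On other tracts: "We will also use this approach for Exploratory Aim 2 when we examine the effect of connectivity deficits in other tracts".

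H3a predicts that WML volume in both CB and UF is related to nonremission on escitalopram, and H3 expects no such relation on placebo. H4a predicts a relation on bupropion for UF and not for CB.

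**The concern.** Tract WML is a component of total WML. If overall burden affects remission, a tract coefficient from a model without overall burden can carry part or all of that effect. Age and vascular risk are only proxies for lesion volume. Stratification balances total WML between arms but leaves the tract-total correlation within each arm untouched.

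What is at stake is the interpretation. Overall burden is the main rival to the focal hypothesis, the sponsor names it, and the segmentation step already measures it. Aim 2 has no analysis that shows how much of a tract estimate remains when the rest of the lesion burden is held fixed. H3a adds little discrimination here, because overall burden would also push CB and UF in the same direction.

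The point concerns tract WML only. It does not extend to the functional-connectivity hypotheses (H3b, H4b).

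**Working it through.** **Inputs from the plan.** 130 evaluable participants (section 4.0). 2:1 allocation (section 9.1), so 130 × 2/3 ≈ 87 on escitalopram and 43 on placebo. Nonremission 0.36, effect 0.45 and covariate share 0.10 (section 15.1).

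**The plan's own figure.** Section 15.1 gives 0.45 as detectable, states no power, and calls it a log hazard ratio within a logistic approach. With a predictor of SD 1 and two-sided 0.05:
- Logistic form: power = Φ(√(n·p·(1−p)·b²·(1−R²)) − 1.96) = Φ(√(130 × 0.36 × 0.64 × 0.45² × 0.90) − 1.96) = Φ(2.336 − 1.96) = 0.65.
- Cox-type form: Φ(√(130 × 0.36 × 0.45² × 0.90) − 1.96) = Φ(2.921 − 1.96) = 0.83.

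So 0.45 can be neither confirmed nor refuted. It serves below only as a scale for effects. Neither calculation includes overall WML.

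**Assumptions not in the documents.** The tract has no effect of its own. Total WML has log OR 0.45 per SD (0.2 as an alternative). The tract-total correlation r is 0.5, 0.7 or 0.85. Age, vascular risk and baseline MADRS correlate 0.5, 0.4 and 0.3 with total WML.

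**Simulation.** Logistic regression, 2,000 trials per setting (Monte Carlo error about 1 point), n = 130, stratified 2:1, all four planned covariates. CB and UF are each r × total plus independent noise.

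| Test (no true tract effect) | False significance at r = 0.5 / 0.7 / 0.85 |
|---|---|
| One tract, escitalopram arm, planned covariates | 9 / 15 / 22% (8-24% over repeat runs) |
| Same, total WML added | 4-6% |
| Interaction, global effect equal in both arms | 5-6% |
| Interaction, global effect on escitalopram only | 9 / 12 / 16% (8-16% over repeat runs) |
| Same, total WML as main effect only | 9 / 12 / 16% |
| Same, total WML and total-by-arm | 5-7% |
| Interaction and arm both significant, one tract | 1-2% (equal effect); 3 / 5 / 7%, up to 8% (escitalopram only) |
| CB and UF both significant, escitalopram arm, no interaction required | about 1 / 4 / 11% (1-12% over repeat runs) |

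With no WML effect at all, the arm test gives 4-5%, the interaction 4-6%, and the two together below 1%. At a global log OR of 0.2 the single-tract rates are about 4-8%, with one smaller run reaching 10% at r = 0.85.

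**H4a.** Taking 36% of 130 gives n ≈ 47. UF is falsely significant in 7 / 9 / 13% of trials. The full predicted pattern (UF significant, CB not) appears in 6.5 / 6.5 / 8.5%, against 4-5% with no WML effect. Section 15.1 expects comparable numbers on each active drug; at n = 87 the pattern rate is about 8-11%.

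**Not simulated.** The bootstrapped indirect effect, splines and multiple imputation. The adjusted runs used total WML rather than volume outside the tract.

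**The case against.** The strongest reply is that the plan already protects itself.

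- Section 15.0 tests the interaction first and only then turns to arm-specific models, so the natural reading is that an escitalopram-arm result follows a significant interaction. On that reading the one-tract rate is 1-8%. This stands, although the plan does not state it as a decision rule.
- H3a names both tracts, so single-tract rates overstate the exposure of the full hypothesis. This stands: 1-12% even without requiring the interaction.
- The global effect is assumed, and section 3.1 notes that studies disagree. This stands: at log OR 0.2 there is little to see.
- The planned covariates already absorb part of the effect. This stands: without them, the escitalopram-arm rates at r = 0.5 and 0.7 were 15% and 26%, against 9% and 15% with them.
- Aim 2 asks about prediction, and an unadjusted tract measure can predict. This stands; only the tract-specific reading is exposed.
- Exploratory Aim 2 looks at other tracts. That could weaken a focal reading, but it does not adjust the CB or UF estimate.

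A reader might infer that any significant CB or UF result from this trial would be an artifact of overall burden, or that the plan rests H3a on an escitalopram-arm coefficient alone. The documents support neither: they give no tract-total correlation and no global effect size, they include a placebo contrast, and near zero correlation the problem disappears.

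**Conclusion.** The concern holds as a gap in interpretation. The omission from the Aim 2 models is plain in the text, and none of the safeguards shows how much of a tract estimate is separate from overall burden. The interaction removes a global effect shared by both arms, but not one confined to escitalopram.

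The size cannot be fixed from the documents. Under the assumptions above it is moderate for a single tract read from the escitalopram arm alone, smaller when the interaction or both tracts are also required, and close to nominal if the global effect is weak. For H4a the inflation is modest at n = 47 and somewhat larger at n = 87, so it should not be called negligible. This is worth correcting, but it does not invalidate the planned analysis.

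**What to change.** Keep the planned models. For H3a and H4a, prespecify one sensitivity analysis that adds continuous, log-transformed WML volume outside the tract (total minus tract) and, in Phase 1, its interaction with drug arm. The main effect alone does not help the interaction test (9 / 12 / 16% with or without it).

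Volume outside the tract is the cleaner covariate because total volume contains the tract. Use the measured volume rather than the high/low stratum: section 9.1 allows the 3.86 mL cutoff to change and a visual rating to replace it. In runs without other covariates (n = 87, r = 0.5 / 0.7 / 0.9), adding only the stratum left 6 / 8 / 13% false significance.

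Beside each planned model, report the tract estimate with and without the added terms, the confidence intervals, and the tract-global correlation. Set no attenuation cut-off and no pass/fail rule: among trials significant in the planned model, the estimate fell by more than a third in 26 / 49 / 61% when the effect was purely global, but also in 4 / 12 / 24% when the tract effect was real. Limit any claim of tract specificity to what the adjusted estimate and its interval support. State that the 10% covariate allowance in section 15.1 does not cover this analysis.

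No new data are needed. The cost is precision. With the logistic formula above at n = 130 and b = 0.45, power falls from about 0.65 (R² = 0.10) to 0.57, 0.41 and 0.26 at R² = 0.25, 0.50 and 0.72, roughly the squares of r = 0.5, 0.7 and 0.85. Simulated power for a true tract effect confined to escitalopram falls from 43 / 38 / 38% to 35 / 27 / 18% in that arm, and from 21 / 19 / 21% to 16 / 13 / 9% for the interaction. These simulated figures are for adjustment by total WML. A wide adjusted interval should be reported as inconclusive.
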